Aim: The aims of this study are to investigate the effects of an individualized exercise programme with and without BCE strategies for community-dwelling frail older people with general fatigue, so as to reduce their fatigue and improve their physical endurance, exercise self-efficacy, and habitual physical activity, while reducing their symptoms of frailty.

Design: A single-blinded three-arm cluster-RCT is proposed to examine the effect of a 16-week individualized exercise programme with or without BCE strategies for frail older people with general fatigue. To explore the way in which the combined intervention will be implemented (42), a focus group with 30 COMB participants (4-6 per group) will be interviewed by a trained research assistant (RA) to identify the strengths, limitations, and therapeutic components of the combined intervention from their perspectives.

Subjects and Settings: Eligibility criteria for district community health centres are those that are funded by the Hong Kong (HK) government and under the supervision of the Social and Welfare Department of HK, and thus that meet a specific set of standard regulations and criteria on environment and practices. All twelve community centres, which provide similar types of community care and social support services for community dwelling older people, have been invited by a convenience method to work as collaborators in this study. The target population of this study are community-dwelling frail older people with general fatigue with a nonspecific cause who will be recruited through the community centres.

Sample size estimation, recruitment procedures, random allocation, and allocation concealment:

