The changes in the mean fatigue scores were -0.58, -5.16, and -2.66 for the control, EXER, and COMB groups respectively, from pre-test to immediately post-intervention in the pilot study. The Cohen's d effect sizes for the EXER and COMB groups were 0.51 and 0.23, respectively; whereas the overall effect size was 0.21. As no similar cluster-RCT has been reported in the literature and the cause of general fatigue is heterogeneous, we assumed that an intra-correlation coefficient would be low (0.01) within each cluster (43). Based on an effect size of 0.21 in the pilot study, and four clusters (community centres) per group with an intraclass correlation of 0.01, a significance level (α) of 0.05, and a power ($1-\beta$) of 0.8 for a two-sided test, the sample size was calculated to be 76 participants per group according to NCSS PASS 14. For a long-term follow-up of 12 months, 285 participants (95 per group) will be recruited after considering an attrition rate of 20%. Using computer-generated random numbers, a biostatistician not affiliated with this study will randomize the centres into either: control, EXER, or COMB. The randomization will be stratified based on the size of the centres. Small-medium centres will be defined as those with < 800 ($n=9$) clients, whereas those with > 800 clients will be defined as large ($n=3$). The number of participants recruited in each centre will be in proportion to the size of the centre (i.e., the total number of clients). We estimate that about 25-50% (4, 16, 44) of the 8,710 members of these centres will be eligible to participate. To avoid selection biases, the allocation to the study groups will be concealed from the researchers until the recruitment of the sample and measurement of the baseline have been completed (please refer to the item 13 in this application for details of the collaborators).

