Participants will be assessed on a variety of outcomes (described below) at week 8 (T1 at mid-term programme), 1 week (T2 immediate effect), 6 and 12 months after the programme (T3 and T4), which will be compared with the baseline assessment (T0). All assessments will be carried out by a part-time RA, regarded as an independent assessor, who will be blinded to the group assignments.

Socio-demographic data: The following data will be collected: 1) age, gender, marital status,

exercise habits, living conditions, and level of education, 2) the participants' health-related information, including cognitive status and medications. Additionally, their levels of comorbidity will be assessed using the Chinese version of the Charlson comorbidity index (C-CCI). The C-CCI score is the sum of the comorbidity and age scores, in which scores of 0, 1-2, 3-4, and > 5 represent the comorbidity level as none, low, medium, and high, respectively⁵⁰. The health services utilization of the parents in the past 12 months and during the study period, such as the number, duration, and causes of hospital admissions and scheduled/non-scheduled clinical visits, will be collected during each measurement time point and will be treated as a co-variate if needed.

Primary outcome measurement: Fatigue will be assessed using the 20-item Chinese Multidimensional Fatigue Inventory (CMFI-20)⁽⁵¹⁾. This scale was validated among 385 local cancer patients. A factor analysis revealed that it contains three factors (namely, physical, mental, and spiritual) with a factor loading ranging from 0.52 to 0.75. The Cronbach's α was between 0.7 and 0.8 for three domains and the total of the CMFI-20 score. It supports the view that the CMFI-20 is a reliable and valid instrument.

Secondary outcome measurements

Physical Endurance will be evaluated using different physical tests. First, the participants' lower-limb and upper-limb strength will be assessed using a 30-second chair stand test⁽⁵²⁾ and a handheld Jamar Hydraulic Hand Dynamometer⁽⁵³⁾, respectively. Their mobility and overall physical endurance will be assessed through the TUG test and by their gait speed (6-m walk).

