Procedures: (*Appendix IV*: Detailed Ethical Considerations; *Appendix V*: CONSORT diagram of the Cluster RCT) Ethical and access approval will be obtained from the Ethics Review Committee of The University and study venues, respectively. Potential participants will be referred to the research team by the collaborators. An RA will screen all potential participants for their eligibility to participate in this study. Written informed consent will then be obtained from all of the participants, to whom all aspects of the study will be explained and questions answered. They will then be interviewed to obtain their health-socio-demographic data, and baseline assessment. After that, the twelve community centres will be randomized to either the control, EXER, or COBM group. Participants from each centre will be placed into their centre's corresponding group to avoid 'contamination' effects across participants. At the mid-term programme, 1 week, 6 months, and 12 months post-intervention, an independent assessor who is blinded to the group allocations will assess the participants' outcomes, which will be compared with the baseline assessment. Focus group interviews will be conducted by the trained RA after the first post-test 1 (one-week post-intervention). Purposive samples of 30 participants from the COMB group will be selected to take part in one interview (4-6 per group). They will be asked to comment on their experiences and (dis)satisfaction regarding the programme, perceptions of its positive/negative aspects, concerns and difficulties in participating and adhering to the programme, and ways of improving the intervention. A semi-structured interview guide will be developed for these interviews, which will be conducted in Cantonese, and all interviews will be audio-recorded for content analysis. Examples of interview questions include: "What are your opinions and comments on your participation in the programme?" and "What are your changes and / or difficulties in adherence to the exercise regimen during and after the 16-week programme?"

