Intervention fidelity and RA training: The PI will train an RA on how to use all of the outcome instruments with reference to the latest user guidelines for the instruments, so that the RA can act as an independent outcome assessor. The RA will practise using all of the instruments, with clinical vignettes and on-site practise. The inter-/intra-rater reliabilities will be evaluated by the intra-class correlations (ICC). Acceptable levels of reliability (ICC > 0.9) will be established by comparing the scores rated by the assessor and the PI prior to the start of the study, and checking them on a monthly basis throughout the data collection period. These procedures are to ensure that quality assessments are performed as intended. The protocols of the exercise and BCE programmes have been developed and tested in the pilot study (14). They will be used to guide the implementation of all interventions in different sub-groups to ensure standardization throughout the study. The pre-intervention practice of the BCE facilitator and the exercise instructor will be supervised by the research team on one or two small groups of older adults with general fatigue. All BCE and exercise sessions must follow the programme protocol and will be run by the same facilitator/exercise instructor to ensure intervention consistency. Intervention fidelity checking will be conducted in the training period and then monthly to bimonthly during the intervention period based on the BCE facilitation/exercise checklist.

Achieving a fidelity rate of > 90% will be considered acceptable based on the recommendations of the NIH Behaviour Change Consortium (59). This is to ensure that all of the interventions are executed by the exercise instructor or the BCE facilitator as intended. Monthly quality control meetings with all research personnel (the exercise instructor, BCE facilitator, and RAs) will be arranged to evaluate their instruction/facilitation skills in this study.

References:

1. Avlund K. Fatigue in older adults: an early indicator of the aging process? *Aging Clin Exp Res.* 2010; 22(2): 100-15.
2. Xue Q-L, Bandeen-Roche K, Varadhan R, Zhou J, Fried LP. Initial manifestations of frailty criteria and the development of frailty phenotype in the women's health and aging study II. *J Gerontol A Biol Sci Med Sci.* 2008; 63(9): 984-90.

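### The monthly intervention quality-control meetings include the RAs and do not exempt the RA who is the blinded outcome assessor: an avoidable risk to the trial's only stated blind

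*Protocol*

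**What the plan says.** The Design paragraph of the protocol describes the blinding in one phrase: "A single-blinded three-arm cluster-RCT is proposed". Instruments and Measures shows whose blind that is: "All assessments will be carried out by a part-time RA, regarded as an independent assessor, who will be blinded to the group assignments". Procedures repeats it for the mid-term and the three post-programme assessments: "an independent assessor who is blinded to the group allocations will assess".

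Intervention fidelity and RA training begins with the training of that RA as outcome assessor. It includes a reliability comparison with the principal investigator before the study starts and then "checking them on a monthly basis throughout the data collection period". The section goes on to the supervision of session delivery and ends with this rule: "Monthly quality control meetings with all research personnel (the exercise instructor, BCE facilitator, and RAs) will be arranged to evaluate their instruction/facilitation skills".

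Allocation is by centre. Procedures states: "Participants from each centre will be placed into their centre's corresponding group". Under Interventions, the behavioural change (BCE) sessions go to COMB only, exercise goes to EXER and COMB, and health talks go to EXER and control.

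The legend of Appendix V lists exercise adherence among the baseline and outcome assessments, for EXER and COMB only.

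**The concern.** The assessor is an RA, and the meeting rule brings in the RAs without qualification. Followed as written, the rule has the assessor meet every month with the exercise instructor and the BCE facilitator to review delivery that differs by arm. A remark that ties a centre to a type of session would inform the assessor about every participant at that centre, not about one person.

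No other blind stands behind this one. Participants and session staff are not described as blinded. The concealment from researchers in the sample size and allocation section ends once recruitment and baseline measurement are complete. If the assessor's blind fails, the follow-up assessments have no stated protection against observer bias.

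**Working it through.** No formula applies and the plan gives no figure to reproduce. The check is a comparison of the passages.

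1. **Is the assessor an RA?** Yes. Instruments and Measures says so, and the fidelity section trains an RA for that role. The assessor is the only RA that the fidelity section introduces before it uses the plural in the meeting rule.

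2. **Is the assessor exempted anywhere?** No. No section of the protocol or SAP limits the meetings to RAs who deliver sessions, or bars the naming of centres or arms. The one RA expressly kept apart from other procedures is the health-talk RA (The Control Condition). No matching sentence covers the assessor.

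3. **What could be learned?** From the allocation of components under Interventions:
   - a centre linked to BCE sessions is COMB;
   - a centre linked to exercise is not control;
   - a centre linked to health talks is not COMB;
   - a centre linked to both exercise and health talks is EXER.

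4. **When?** All four follow-up assessments (T1 to T4) come after allocation. T1 is at week 8, while sessions are running. The protocol gives no start date for the meetings. Assuming one every 4 weeks from the start of the 16-week programme, 8/4 = 2 would fall by week 8 (1 if the second comes after the T1 visit) and 16/4 = 4 by the end of the programme.

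5. **Which outcomes?**
   - Run by the assessor: chair stand, grip dynamometer, TUG and gait speed.
   - Partly run by the assessor: the frailty index. Two of its five criteria, walking speed and grip, are performance measures. They overlap with two of the four tests above, so they are not separate exposures.
   - Self-reported: the CMFI-20 (primary), exercise self-efficacy, PASE-C and the depression scale. Knowledge of the arm could act here only through how the questions are put and recorded.

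6. **How large a bias?** Not computable. The documents give no probability that a centre is linked to an arm in a meeting and no SD for the performance tests.

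7. **Exercise adherence.** Instruments and Measures gives all assessments to the blinded RA, while the Appendix V legend lists adherence for two arms only. An assessor who collected it at some centres and not at others could tell the control centres from the exercise centres. The diagram itself is not available, and no section says who collects this item.

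**The case against.** The strongest reply is that the meeting sentence is not meant literally. Its stated purpose is to review instruction and facilitation skills, and the assessor does neither. Its list of roles leaves out the physiotherapist and the principal investigator, so *all* is loose wording. The assessor's quality control is a separate monthly reliability check, and two sections state the assessor's blinding directly. Other RAs have speaking tasks, such as health talks and focus groups, and could account for the plural. The sessions "will be run by the same facilitator/exercise instructor to ensure intervention consistency", so a skills review need not name a centre.

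Much of this stands. It makes the narrower reading reasonable and means that attendance by the assessor is not established. It does not settle the matter. Even if the list of roles defines who attends, RAs are on it without qualification, and the assessor is the RA that the same section has just described. The separate reliability check shows that the assessor has no need to attend; it does not say that the assessor stays away.

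On adherence, it is fair to reply that the item is not among the outcomes described in Instruments and Measures, so the assessor may never have been meant to collect it. That is why clarification is enough.

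Two stronger readings are tempting. A reader might infer that the plan will unblind the assessor. The text shows only that it could. A reader might also infer that the assessor runs or transcribes the COMB focus groups, since the RA for those tasks is not identified. That inference rests on silence alone, and Procedures uses different labels for the assessor and the interviewer, so it is not relied on here.

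**Conclusion.** The point holds as an avoidable risk. A stated attendance rule, taken at its word, works against the only blinding that the trial describes, and allocation by centre makes any disclosure reach a whole centre. Harm needs three steps: the assessor attends, a centre is linked to its sessions, and scoring or test administration then shifts. The documents establish none of these, so confidence is moderate.

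The consequences fall mainly on secondary outcomes, namely the four performance tests and the frailty criteria that share two of their measures. The primary outcome is only partly exposed, and nothing here shows that the primary comparison is biased. The conclusion assumes that *RAs* may include the assessor, which the text permits but does not compel. The change should be made because the exposure serves no purpose and is simple to remove.

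**What to change.** In Intervention fidelity and RA training, add one sentence: the blinded outcome assessor does not attend the intervention quality-control meetings, and the assessor's monthly reliability check is held separately. Nothing is lost, since that check already covers the assessor's quality control.

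In Instruments and Measures, add one line: exercise adherence in EXER and COMB is collected by existing team members other than the assessor. The Control Condition keeps the health-talk RA out of other procedures, so this has to be someone else on the team.

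The cost is two sentences and a minor reallocation of tasks. Sample size, visits and analysis do not change. Other routes to disclosure remain, such as participants mentioning their sessions at an assessment.

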Appendix I: Figure of HAPA

[figure not shown]

Figure 1: The Health Action Process Approach (HAPA).

Appendix II: Overview of the combined intervention

		@week 8 (half-way point of the intervention)			@1 week after the intervention + Focus groups for 30 participants	@6 months & 12 months after completing the entire programme
		T ₀	T ₁	T ₂	T ₃ and T ₄	
Week		1-2	3	4-16	2 and 6 months after completing of entire programme	
HAPA Phases	Phase 1 Goal Initiation	Phase 1 Goal Initiation	Phase 2 Plan Formation	Phase 3 Action Execution		
	Behavioural Change Enhancement Programme	2 sessions	1 session	
 3 sessions – 1 session per month in weeks 4, 8, and 12 (i.e., the 1st week of each month in the action execution phase) 	
 2 booster sessions – 1 session 2 months after completing the entire programme and 1 session 6 months after completing the entire programme 	
Intervention Components	Exercise			
 12-week centre-based exercise programme on 1) balance 2) resistance exercises, and 3) aerobic training Physiotherapist tailor-made individualized exercise regimen for participants based on an individual physical assessment at weeks 4, 8, and 12 	
 Continue to regularly practise the exercises 	

Appendix III: HAPA Based-behavioural Change Enhancement Programme Protocol

Expected outcomes: The participants will:

- 1) demonstrate a sense of self-control and confidence in managing their fatigue-related health issues,
- 2) agree to gradually exceed their perceived energy limits and recondition their bodies through participating in exercise according to their own exercise regimen.

Size of group: Maximum of 10.

Phases	Session No	Aims	Contents
Goal Initiation	1	
 • To establish the intention to adhere to strategies that address issues related to fatigue • To understand the expected outcomes of the programme • To increase awareness of the negative impacts of unmanaged fatigue • To strengthen self-efficacy 	
 • To get the participants to share their experiences with fatigue • To explain the expected outcomes of the programme and how these outcomes can match the personal goals of the participants • To introduce the participants to the impacts of unmanaged fatigue on physio-psychosocial wellbeing • To introduce the participants to the deconditioning model of fatigue (i.e., avoiding physical activity exacerbates fatigue-related physical symptoms) • To discuss the participants' intention to complete the programme
	2		
 • To introduce the connection between exercise and fatigue • To understand the expected outcomes in older people resulting from regular exercise • To recognize correct / incorrect beliefs about exercise for older people • To recognize and overcome barriers to staying or becoming physically active • To identify the negative impacts of leading a sedentary lifestyle
Plan Formulation	3	
 • To create an action plan and coping plan for adhering to the exercise regimen • To set sub-goals 	
 • To evaluate the participants' current preferences relating to exercise • To set achievable sub-goals with the participants based on the physical and cognitive abilities of individuals • To reassure the participants that the final goals will be divided into several achievable sub-goals according to an individual's progress throughout the programme • To create a detailed action plan of when, where, and how to practise the desired action • To identify an alternative coping plan
Action Execution	4	
 • To encourage action execution • To continue strategies that can enhance the participants' self-efficacy, which include 
 • obtaining performance accomplishments • generating social persuasion • gaining vicarious experience • perceiving the positive physiological and emotional responses of engaging in regular exercise 	
 • To self-evaluate levels of compliance with the action plans and the achievement of the sub-goals, so as to let the participants experience success by achieving the (sub) goals • To provide positive feedback and encouragement from peers and the BCE facilitator • To observe peers with similar physical and psychological difficulties related to fatigue adhering to the action plan, participants will be provided with chances to learn about the successful experiences of their peers during the sharing sessions • To continue to refine the sub-goals and the action and coping plans according to the progress, if necessary • To promote positive perceived responses (such as vitalization-enjoyment and improved endurance) after exercise • To guide the participants to develop their own plan for the sustainability of their actions in the future • To round up the participants in the final session (S6) and encourage them to continue the action in the future
	5		
	6		
	Booster Session at 2 nd and 6 th Month		
 • To recap all strategies used in previous sessions during action execution, so as to reinforce the participants' self-efficacy • To review and modify long-term goals / action plans / exercise regimens, etc. • To practise exercises together • To share experiences and thoughts related to 
 - Compliance with regular exercise - Fatigue management

Appendix IV: Detailed Ethical Considerations

[figure not shown]
The principle of protecting research subjects in accordance with the Helsinki Declaration will be observed. The data will be kept confidential in accordance with Hong Kong's Privacy Ordinance. All of the research personnel involved will work closely together to monitor the occurrence of untoward effects on the participants. Standard guidelines for managing symptoms of intolerance will be used. For example, a target heart rate (THR) will be identified for each participant. Those at the beginner level will be advised not to exceed 50% to 60% of their THR, with the figure being 60% to 70% for those at the intermediate level. The physiotherapist / the PI (a registered nurse) will give individual participants advice on an ad hoc basis to ensure their safety. Below please see an example of the safety guidelines for preventing falls while exercising at home.

Guidelines for managing older people who fall while doing exercises at home:

After slipping and falling, elderly people should take the following steps to help themselves:

1. Keep calm.
2. Assess the level of injury; move slowly if not severe.
3. Move along the ground to walls or stable furniture, then climb up with the support of the furniture.
4. If you cannot stand up, you may make a call by using the Personal Emergency Link Service / opening the main door and loudly asking for help.
5. Clean the wound first if you get an abrasion.
6. Consult a doctor quickly if you note any problems. You may have a fracture if you have difficulty moving or are in severe pain, even without any obvious wound.
7. All fall accidents should be reported to the research team.
8. In all cases, a follow-up call by phone will be conducted by the PI, who is a registered nurse.

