Interventions: (*Appendix II:* Overview of the combined intervention) A 16-week programme with a combination of exercise and the BCE programme (plus two booster BCE sessions will be held at 2 and 6 months after the programme) will be arranged for the COMB group. Another 16-week programme with a combination of exercise and health talks will be arranged for the EXER group, whereas participants in the control group will attend only the health talks with no other intervention. Two added health talks will be arranged at 2 and 6 months after the programme for the EXER and the control groups. To control the group and social interaction effects of the BCE programme for the COMB group, the number and timing of the health talks for the other two groups will be similar to those in the BCE sessions. All face-to-face sessions will have < 10 participants to maintain good interactions between the participants and the exercise instructor / BCE facilitator/ health talk speakers.

The behavioural change enhancement (BCE) programme in the COMB group (Appendix III: BCE programme protocol) aimed at motivating the participants to develop the intention to actively manage their fatigue; and to encourage them to gradually exceed the perceived limits of their energy and to recondition their bodies by participating in exercise according to their individual exercise regimens. The BCE programme was designed based on the HAPA model and was piloted by the PI

(14). It consists of three phases with six face-to face one-hour sessions plus two booster BCE sessions at 2 and 6 months. The first three weekly sessions will be arranged during the ‘goal initiation’ and ‘planning’ phases. The remaining three sessions and two booster sessions will be offered once per month in weeks 4, 8, and 12 during the programme; and at 2 and 6 months after the programme during the ‘action execution’ phase.

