Exercise intervention in the EXER and the COMB groups: A weekly 45-60 minute centre-based exercise programme, which designed according to the American Heart Association’s recommendations on exercise for older people (48), will be arranged from weeks 4-16 during the execution phase. This programme will consist of balance training, such as sideways walking (15-20 minutes); resistance exercises, such as using resistance bands to improve muscle strength in both the upper and lower limbs (10-20 minutes); aerobics training, such as walking (10 minutes) and with 10 minutes of warm-up and cool-down exercises at the beginning and at the end. All participants will receive circuit training with set exercises, but the dosage of different components will be tailor-made for each participant based on his/her physical conditions. The first assessment will be in week 4 (i.e., the first week of the exercise programme), and subsequent monthly assessments will be held in weeks 8 and 12 by a physiotherapist. The dosage of exercises will gradually increase by increasing the number of repetitions, the duration of the exercises, and also by using progressively heavier wrist and ankle weights maintained at approximately 12-14 on the Borg Rate of Perceived Exertion Scale(28, 49), based on the participants’ progress. The dosage of exercise recommended to each participant by the physiotherapist will be recorded. Demonstrations and return demonstrations will be performed during the training to ensure that the participants are able to do the exercises properly. A compact disc and a pamphlet describing the different types of exercises used in this programme will be disseminated to all participants to encourage them to continually practice their exercises at home for approximately 30 minutes at least 3 times per week. Although this set of exercises was used in the pilot study with no reports of adverse effects, safety guidelines on exercise for older people will be discussed with all of the participants.

The Control Condition: Participants in the control and EXER groups will attend centre-based health talks on the management of different health issues with the exception of fatigue. Another RA, who will not be involved in other procedures of this study, will run the health talks.

Instruments and Measures

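### Falls are not an outcome at any visit and no harms analysis is planned, so apart from medically attended falls the trial cannot compare falls between arms on an equal basis

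*Protocol*

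**What the plan says.** Four parts of the plan bear on falls.

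- **Safety text (Protocol, Appendix IV).** It opens with a general duty: "All of the research personnel involved will work closely together to monitor the occurrence of untoward effects on the participants". It then introduces one illustration, "Below please see an example of the safety guidelines for preventing falls while exercising at home", under the title "Guidelines for managing older people who fall while doing exercises at home". Item 7 of that list reads "All fall accidents should be reported to the research team", and item 8 adds a follow-up telephone call in every case.
- **Interventions (Protocol).** Home practice is set out under "Exercise intervention in the EXER and the COMB groups". The same section ends by saying that "safety guidelines on exercise for older people will be discussed with all of the participants". For the third arm, "participants in the control group will attend only the health talks with no other intervention".
- **Measurements (Protocol, Instruments and Measures).** Fatigue is primary. The secondary outcomes are physical endurance, exercise self-efficacy, frailty status, physical activity and depressive mood. The Appendix V footnote repeats these and adds exercise adherence for EXER and COMB. Neither list contains falls or adverse events. Under socio-demographic data, health-service use is collected at each time point, including "the number, duration, and causes of hospital admissions" and clinic visits, as a covariate if needed.
- **SAP.** Mixed models are planned for the outcome assessments and for exercise attendance and adherence. Health-service use appears only in the list of possible covariates. Falls and other harms have no analysis.

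**The concern.** The trial gives balance and resistance training to frail people over 70 and follows them for 12 months after the programme. The protocol itself foresees falls, since they are its chosen example of safety guidance. COMB participants are also encouraged, through the BCE programme, to go beyond their perceived energy limits; that aim is not stated for EXER.

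The plan would therefore collect some fall reports, but through a route tied to an activity that control participants are not prescribed, with no definition, form, schedule or denominator. At the end the investigators could say how many home-exercise falls were reported to them. They could not say how often participants fell in each arm. A safety statement about the exercise programmes would rest on an absence of systematic enquiry, and no later analysis can supply falls that nobody asked about.

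**Working it through.** No stated figure is in dispute, so the main check compares the possible routes by which a fall could enter the data.

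| Route | EXER and COMB | Control | Planned use |
|---|---|---|---|
| Item 7 of the Appendix IV guidance | Falls during home exercise, self-reported | No home exercise prescribed | None stated |
| General monitoring of untoward effects | Yes, method not stated | Yes, method not stated | None stated |
| Causes of admissions and clinic visits, each time point | Yes | Yes | Possible covariate |
| Falls question at T1 to T4 | None | None | None |

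**Is item 7 tied to the exercise arms?** The guidance concerns home exercise, and the SAP compares home-exercise adherence between EXER and COMB only. The sentence on discussing safety guidelines refers to all participants, but the same section says that all participants receive circuit training, which control does not. In that section the phrase most naturally means everyone in the two exercise arms. This is an inference; the text does not state it.

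**How much could item 7 capture even there?** Home practice is suggested for about 30 minutes at least 3 times a week: 3 × 0.5 h = 1.5 h, and 1.5/168 = 0.9% of the week at that minimum. Read literally, the route would miss falls at other times in the exercise arms as well.

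**Is general monitoring even across arms?** Contact is not. EXER and COMB have weekly exercise sessions in weeks 4-16 and physiotherapist assessments in weeks 4, 8 and 12. The control arm's health talks are run by an RA who has no part in other procedures.

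**What would equal collection deliver?** Inputs from the protocol's sample size section: 76 evaluable per arm, 76/(1 − 0.20) = 95 recruited, four centres per arm, ICC 0.01. Assumptions not in the documents: a control faller risk of 20-40%, and the same ICC for falls. EXER and COMB are pooled (152 against 76).

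- Design effect: 1 + (76/4 − 1) × 0.01 = 1.18. Effective numbers: 76/1.18 = 64.4 and 152/1.18 = 128.8.
- 95% half-width for the risk difference, with equal risk p in both groups: 1.96 × √[p(1 − p)(1/76 + 1/152) × 1.18]. At p = 0.20 this is 0.120.
- Power, two-sided 5%: Φ[(|p1 − p2| − 1.96 × SE0)/SE1], with SE0 from the pooled risk and SE1 from the separate risks, at the effective numbers. For 0.20 against 0.15: SE0 = 0.0569, SE1 = 0.0589, giving Φ(−1.04) = 0.15.

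| Assumed control risk | Power, risk ratio 0.75 | Power, risk ratio 1.5 | 95% half-width (points) |
|---|---|---|---|
| 20% | 15% | 31% | 12.0 |
| 30% | 21% | 52% | 13.7 |
| 40% | 29% | 75% | 14.7 |

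These use normal quantiles with only twelve centres, so they are somewhat optimistic.

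**The case against.** The strongest reply is that falls are not invisible in the control arm. Admissions and clinic visits are recorded with their causes at each time point and without restriction by arm, so the falls that led to medical care can surface anywhere. The duty to monitor untoward effects is also general, the falls text is offered as one example and not as the full safety guidance, and the pilot reported no adverse effects with this set of exercises.

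Much of this stands. A reader might infer that item 7 is the only way a fall can be recorded, and that the control arm would record almost none. The documents do not support that, because medically attended falls have a route in all arms. A reader might also infer that the exercise arms will look more harmful. That would require item 7 reports to be tabulated by arm, which neither document proposes. Nor can a contrast be drawn between all fallers in the exercise arms and almost none in control: if item 7 covers only home exercise, most exercise-arm falls escape it too.

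What does not stand is that these routes amount to a usable comparison. Monitoring has no stated method and staff contact differs by arm. The service-use data are destined for covariate adjustment: under the SAP, service use that differs significantly between groups may be adjusted for, and nothing provides for reporting such a difference as a possible harm. Falls without medical care are not asked about at all.

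It is also fair to object that collecting falls would not settle whether exercise raises or lowers them. The power figures confirm this. The gain is an even-handed description with an interval.

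**Conclusion.** The point holds in a limited form. Falls are not an outcome at any visit, no harms analysis is planned, and the one explicit reporting instruction concerns an activity prescribed only to EXER and COMB. Apart from medically attended falls that may be found among the causes of admissions and visits, falls cannot be compared between arms on an equal basis.

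This is a gap in collection and reporting and does not bias any planned estimate. Its size in falls missed cannot be calculated, because the documents give no fall rate. The conclusion rests on two readings: that the home-exercise guidance is addressed to the exercise arms, which is inferred, and that service-use causes are recorded for all participants, which the absence of any restriction by arm supports. If control participants also received the guidance, the conclusion would not change, since it would still concern exercise that they are not prescribed. The change is a cheap improvement that should be made before data collection, because the missing information cannot be recovered afterwards.

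**What to change.** 1. **Protocol, Instruments and Measures.** Add falls and injurious falls, each with a single definition. At T1 to T4 the blinded assessor asks every participant in all three arms, in identical words, how many of each occurred since the last visit, in the same interview as service use. The question need not ask what the participant was doing, which helps protect the blind.
2. **SAP.** Add a descriptive table by arm of falls, injurious falls and fall-related admissions, with the number of participants asked at each visit. State that it is not a powered test.
3. **Home-exercise fall reports.** Keep them as a separate listing and do not use them for between-arm comparison.

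The cost is two questions at four existing visits, one table and one listing. Exercise and clinical management are unchanged. The main weakness is recall. The intervals are about 8 weeks to T1, about 9 weeks to T2 (week 17 less week 8), and about 6 months each to T3 and T4. Recall over up to 6 months is imperfect. It may also differ by arm, because participants know whether they are exercising and those given the falls guidance may be more alert to falls. The report should say so.
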